5.2.6. Conventions

Unless otherwise specified, the following conventions will be applied to all analyses:

- 1 year = 365.25 days. Year is calculated as (days/365.25) rounded up to 1 significant digit;
- 1 month = 30.4375 days. Month is calculated as (days/30.4375) rounded up to 1 significant digit;
- Age will be calculated as the integer part of (date of randomization date of birth + 1)/365.25;
- 1 pound = 0.454 kg;
- 1 inch = 2.54 cm;
- Time-to-event (TTE) or duration of event endpoints will be based on the actual date rather than the associated visit date;
- Missing efficacy or safety data will not be imputed unless otherwise specified;
- For laboratory results collected as < or > a numeric value, 0.0000000001 will be subtracted or added, respectively, to the value;
- For safety analyses, percentages will be calculated based on the number of patients in the analysis population in each treatment group;
- For by-visit observed data analyses, percentages will be calculated based on the number of patients with nonmissing data as the denominator unless otherwise specified;
- For TTE data, the summary statistics and descriptions will include Kaplan-Meier plots and/or life tables;
- For other continuous endpoints, the summary statistics will include mean, standard deviation, median, and range (minimum and maximum);
- For categorical endpoints, the summary statistics will include counts and percentages;
- Medical history will be coded using the MedDRA version in use at the time of database lock;

- Prior therapies and concomitant medications will be coded using the World Health Organization (WHO) Drug Dictionary.
- The terms "patients", "participant", and "subjects" may appear in this document and are considered interchangeable."

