MDV3100-14 (PROSPER): A phase 3, randomized (2:1), double-blind, placebo-controlled efficacy and safety study of enzalutamide (160 mg daily) was conducted in 1401 men with nonmetastatic, castration-resistant prostate cancer and a PSA doubling time of 10 months or less, continuing on androgen-deprivation therapy received enzalutamide or placebo once daily. The primary end point was MFS. The median MFS was 36.6 months in the enzalutamide group versus 14.7 months in the placebo group (hazard ratio for metastasis or death, 0.29; 95% confidence interval, 0.24 to 0.35; $P < 0.001$). The time to the first use of a subsequent antineoplastic therapy was longer with enzalutamide treatment than with placebo (39.6 vs. 17.7 months; hazard ratio, 0.21; $P < 0.001$; such therapy was used in 15% vs. 48% of patients) as was the time to PSA progression (37.2 vs. 3.9 months; hazard ratio, 0.07; $P < 0.001$; progression occurred in 22% vs. 69% of patients). At the third interim and final analysis of OS, conducted when 466 deaths were observed, a statistically significant improvement in overall survival was demonstrated in patients randomized to receive enzalutamide compared with patients randomized to receive placebo with a 26.6% reduction in risk of death (hazard ratio = 0.734; 95% CI: 0.608, 0.885; $p = 0.0011$).

In addition to the clinical studies in men with metastatic CRPC, a key clinical study evaluated enzalutamide monotherapy in men with hormone-sensitive prostate cancer as follows:

9785-CL-0321: A phase 2, open-label, single-arm, multicenter, efficacy and safety study of enzalutamide monotherapy (160 mg daily) was conducted in 67 patients with hormone-naïve prostate cancer for whom androgen deprivation therapy was indicated. The primary objective was to determine the incidence of patients with a $\geq 80\%$ PSA response at week 25. Secondary objectives included evaluation of safety and tolerability; exploratory objectives included evaluation of lipids, body mass, bone density, markers of bone turnover, and quality of life. At week 25, the PSA response was 93% (62 of 67 patients; 95% CI, 86%-99%) and the median PSA decrease was 99.6%.

Including these studies, approximately 8000 subjects and patients have been enrolled worldwide in completed and ongoing clinical trials evaluating enzalutamide, including more than 7000 men with prostate cancer.

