6.1.1.1. Primary Analysis

The primary efficacy analysis will compare MFS based on BICR assessment between enzalutamide in combination with leuprolide versus placebo in combination with leuprolide using a 2-sided stratified log-rank test as described in Section 5.1. The primary population for analysis will be the ITT population. Strata will be based on those specified in the randomization system.

MFS is defined as the time in months between randomization and the earliest objective evidence of radiographic progression as determined by BICR, or death due to any cause without evidence of radiographic progression, whichever occurs first. Radiographic assessment of soft tissue disease will be according to RECIST v1.1 on CT scan or on MRI. Additional bone lesions will be assessed separately using radionuclide bone scans.

Table 6 summarizes the protocol-specified rules for the radiographic evidence of progression.

Tissue Type	Method of Assessment	Schedule	Comment
Bone	A whole-body radionuclide bone scan will consist of 5 regions including skull, thorax, spine, pelvis, and extremities. Radiographic progression for bone disease is defined as the appearance of 1 or more metastatic lesion on bone scan. When bone lesions are found in a single region, confirmation with a second imaging modality (plain film, CT, or MRI) will be required. Appearance of metastatic lesions in 2 or more of the	Screening and every 24 weeks thereafter (earlier if progression is clinically suspected) until radiographic progression is confirmed by independent central radiology review	All study films should be read locally at the study site and submitted to the central imaging unit for independent central radiology review

Table 6.	Protocol-Specified Ru	ules for the Radiogran	hic Evidence of Progression
	riotocor specifica in	and for the reading rup	

Tissue Type	Method of Assessment	Schedule	Comment
	5 regions on a bone scan will not require confirmation with a second imaging modality.		
Soft Tissue	Assessment of soft tissue disease will be done by CT or MRI. Radiographic progression for soft tissue disease is defined by RECIST 1.1.		

 Table 6.
 Protocol-Specified Rules for the Radiographic Evidence of Progression

CT = computed tomography; MRI = magnetic resonance imaging; RECIST 1.1 = Response Evaluation Criteria in Solid Tumors version 1.1.

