6.5. Exploratory Endpoint(s)

6.5.1. Progression-Free Survival on First Subsequent Therapy (PFS2)

PFS2 is defined as the time in months from the date of randomization to the first occurrence of investigator-determined disease progression (PSA progression, progression on imaging, or clinical progression) or death due to any cause, whichever occurred first, while the patient was receiving first subsequent therapy for prostate cancer.

PFS2 (months) = [date of event or censoring – start date +1]/30.4375

A patient will be considered to have an event if

1. the patient had objective PD on or prior to the start of the first subsequent antineoplastic therapy, AND had investigator-determined disease progression (PSA progression, progression on imaging, or clinical progression) after the start of the first subsequent antineoplastic therapy)

OR

2. the patient died.

If there are multiple therapies within a regimen with different start dates, the earliest start date will be utilized. PFS2 will be analyzed using a 2-sided stratified log-rank test. The HR and 95% CI will be provided. Kaplan-Meier estimates will be presented by treatment arm with the median and 95% CIs.

The censoring and event date options to be considered for PFS2, each corresponding censoring reason and its hierarchy are presented in Table 9. Frequency (number and percentage) of patients with an event (PSA progression, progression on imaging, clinical progression after next line treatment or death) and censoring reasons will be presented by treatment arm.

Scenario	Date of Event/ Censoring	Event/ Censoring Reason/ Censoring Hierarchy
(No PD ^a) and (no death)	Date of lastadequate tumor assessment ^b documenting no PD	Censored/ No PD/ 1
(No PD ^a) and death	Date of death	Event (Death)
(PD ^a date > NTX ^c start date) and (no death)	Start date of NTX ^c	Censored/

Table 9.Outcome, Event Dates, Censoring Reasons and Hierarchy for PFS2
Analyses

Scenario	Date of Event/ Censoring	Event/ Censoring Reason/ Censoring Hierarchy
		Start of new antineoplastic therapy before PD/ 2
$(PD^a date > NTX^c start date)$ and death	Date of death	Event (Death)
(PD ^a date \leq NTX ^c start date) and (PD2 ^d date is non-missing)	Date of PD2 ^d	Event (PD after start of first subsequent antineoplastic therapy)
(PD ^a date \leq NTX ^c start date) and (no PD	2 ^d) and (no death)	
• If [withdrawal of consent in the end of study page]	Withdrawal of consent date in the end of study page	Censored/ Withdrawal of consent/ 3

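### SAP 5.2.6 rounds months and years up to one significant digit. This is wrong as written, probably a slip for one decimal place, and should be corrected before the final OS analysis.

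*SAP*

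**What the plan says.** The list in SAP 5.2.6 (Conventions) opens with its scope: "Unless otherwise specified, the following conventions will be applied to all analyses". It then defines the two time units. For months: "Month is calculated as (days/30.4375) rounded up to 1 significant digit". For years: "Year is calculated as (days/365.25) rounded up to 1 significant digit". The list does not say whether this applies to each patient's analysis time or only to printed results.

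The primary endpoint takes its unit from this list: "MFS is defined as the time in months between randomization and the earliest objective evidence of radiographic progression as determined by BICR" (SAP 6.1.1.1). Time to PSA progression, time to new antineoplastic therapy and OS are also defined in months (SAP 3.2.1.2 to 3.2.1.4). None of the four has its own conversion formula.

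Other parts of the SAP do not fit the rounding rule:

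- PFS2 has its own formula, with no rounding: "PFS2 (months) = [date of event or censoring – start date +1]/30.4375" (SAP 6.5.1).
- The PSA doubling time formula in SAP 5.2.5 is also unrounded.
- SAP 6.7.4 groups treatment durations at 6, 12, 24, 36, 48, 60 and 72 months.
- The list in SAP 5.2.6 itself ties these endpoints to calendar dates: "Time-to-event (TTE) or duration of event endpoints will be based on the actual date rather than the associated visit date".

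No other section corrects the rounding wording.

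**The concern.** Read literally, the rule puts every time above 10 months on the next multiple of ten. SAP 5.2.12 plans medians, quartiles and time-point probabilities by Kaplan-Meier. If each patient's time were rounded up first, two things would happen:

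- Events would be moved later, by up to ten months.
- Men censored within a ten-month band would count as at risk for every event in that band.

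Both push the estimated survival curve upwards.

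The primary MFS analysis is complete (Protocol 3.1 and 18.1), so the live question is the final OS analysis at 271 deaths. A programmer cannot sensibly follow the sentence as it stands. The choice is then between an undocumented interpretation and a deviation to be described in the study report.

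**Working it through.** **1. The plan's own design figures.** Inputs from SAP 5.1.1: control median 55 months, hazard ratio 0.58, 142 events in the two blinded arms, two-sided alpha 0.05. The Schoenfeld formula needs 142 events for 90% power. With 142 events it gives power of 90.1% at alpha 0.05 and 85.9% at alpha 0.03. The difference in medians is 55/0.58 − 55 = 39.8 months. All of these agree with the SAP, and none depends on the rounding rule.

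**2. The rule applied to single values.**

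| Months | Up, 1 significant digit | Nearest, 1 significant digit | Up, 1 decimal place |
|---|---|---|---|
| 14.7 | 20 | 10 | 14.7 |
| 36.6 | 40 | 40 | 36.6 |
| 55 | 60 | 60 | 55.0 |
| 94.83 (= 55/0.58) | 100 | 90 | 94.9 |

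The first two values are medians of an earlier enzalutamide trial in castration-resistant disease (Protocol 1.2) and serve only as illustrations. The values 12, 24, 36, 48 and 72, used as cut-points in SAP 6.7.4, cannot occur in the second or third column.

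**3. Expected size by hand, if patient times are rounded up.** A landmark that is not a multiple of ten is then read at the multiple of ten below it. For an exponential control arm S(t) = 2^(−t/55):

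- 2 years: S(24) = 0.739 is replaced by S(20) = 0.777.
- 3 years: S(36) = 0.635 is replaced by S(30) = 0.685.
- 4 years: S(48) = 0.546 is replaced by S(40) = 0.604.
- 5 years: 60 is itself a boundary, so S(60) = 0.469 moves only through censoring.
- Median: S(50) = 0.533 and S(60) = 0.469, so the rounded curve first falls below one half at 60 months.

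**4. Simulation.** 350 men per arm, exponential times, control median 55 months, hazard ratio 0.58, cut-off at month 90. The cut-off is an assumption, taken from the study duration in Protocol 3.4. Accrual was uniform over 42 months (also an assumption, 400 trials, 5% loss by 4 years) or followed the table in Protocol 10.7 (300 control arms).

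| Control arm | Unrounded | Rounded up, uniform accrual | Rounded up, Protocol accrual |
|---|---|---|---|
| Mean median (months) | 55.4 / 55.3 | 61.3 | 62.0 |
| S(36) | 63.4% / 63.6% | 68.6% | 68.6% |
| S(48) | 54.6% / 54.7% | 60.5% | 60.6% |
| S(60) | 47.1% / 47.0% | 48.0% | 48.5% |

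The first figure in the unrounded column is for uniform accrual, the second for Protocol accrual. With rounding up to one decimal place (uniform accrual) the median stays at 55.4 and S(36) at 63.4%.

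**5. Tests and hazard ratio.** The mean log-rank z moves from −4.90 to −4.88 (uniform accrual) and from −4.65 to −4.64 (Protocol accrual). The mean hazard ratio is 0.580 unrounded. After rounding it is 0.581 with Efron ties and 0.592 with Breslow ties. SAP 6.1.1.1 specifies the exact method in SAS, which Efron approximates much better than Breslow when ties are heavy.

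**6. Dependence on the cut-off.** The month-90 cut-off gives about 312 events in the two blinded arms, against the planned 142. When the simulation is cut at 142 events (about month 50), the unrounded control median is not reached in 75% of trials. The 3-year shift is then larger: 63.7% to 72.6%.

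**7. OS, by hand.** Protocol 10.7 assumes 80% control survival at 5 years. If survival is exponential (an assumption), S(t) = 0.8^(t/60). The 3-year rate of 0.8^0.6 = 87.5% would be read as 0.8^0.5 = 89.4%. The 4-year rate of 0.8^0.8 = 83.7% would be read as 0.8^(2/3) = 86.2%. The effect of censoring comes on top.

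**The case against.** The strongest reply is that nobody would program this rule. The same list bases time-to-event endpoints on actual dates, the exposure categories need finer months, and the PFS2 and doubling-time formulas simply divide. The SAP never says that patient times are replaced by rounded ones before Kaplan-Meier or Cox. If rounding applies to display only, the survival probabilities do not change and only printed times are coarsened. If one decimal place is meant, nothing material changes. All of this stands, and it is why the point is minor. It does not make the sentence right. The rule is worded as a calculation, applies to all analyses by default, and is contradicted rather than corrected elsewhere.

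A reader might infer more than the documents support:

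- **That every time-to-event endpoint is affected.** PFS2 has its own unrounded formula, and the default gives way wherever something else is specified.
- **That the treatment effect or the tests are distorted.** A shift in the hazard ratio to 0.592 appears only with Breslow ties, which are not the SAP's method. The log-rank statistic hardly moves.
- **That the completed MFS results are wrong.** Nothing in the documents shows that the literal rule was ever applied.

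**Conclusion.** The wording is an error, most likely one decimal place miswritten as one significant digit. The words for rounding up are a second, smaller fault, because they round in one direction even at one decimal place.

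The harm is conditional on the literal rule being applied to patient-level times. In that case the 3-year MFS rate in the control arm is overstated by about 5 percentage points (68.6 − 63.6) and the median by about 6 to 7 months (61.3 − 55.4 = 5.9; 62.0 − 55.3 = 6.7). Both figures assume exponential times with the design parameters and a month-90 cut-off, and they change with the cut-off. For OS the hand calculation gives about 2 to 2.5 points at 3 and 4 years.

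Event counts, power, alpha and the formal tests do not depend on this point. Severity: minor.

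**What to change.** Replace the rounding phrase for both months and years in SAP 5.2.6 with one statement, for example: *Time-to-event and duration variables are analysed unrounded, as days/30.4375 (months) or days/365.25 (years); values are rounded to one decimal place for display only.*

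The PFS2 and PSA doubling-time formulas can stay as they are, since they already divide without rounding. The change should be made before the final OS analysis. It costs one line in the SAP and has no analytical downside. If any completed output did use rounded patient times, the study report should say so. If none did, a short note confirming this closes the matter.

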3.5. Safety Endpoints

Safety will be assessed through adverse event (AE) reporting, laboratory and vital sign assessments. AEs will be graded by the investigator according to the Common Terminology Criteria for Adverse Events (CTCAE) version 4.03 and coded using the Medical Dictionary for Regulatory Activities (MedDRA) version in use at the time of database release.

Safety endpoints will be summarized based on the on-treatment period, modified treatment period, or re-initiation treatment period as specified.

On-Treatment Period

The on-treatment period is defined as the time from the date of first dose of study treatment through a minimum of 30 days after last dose of study treatment, or the start day of new antineoplastic drug therapy -1 day, where the last dose of study treatment is the final dose after any suspension period due to undetectable PSA. Adverse events occurring on the same day as the first dose of study treatment will be considered to have occurred during the on-treatment period. All other assessments which occur on the same day as the first dose of study treatment will be considered baseline assessments (see Section 3.5).

Safety data collected outside the on-treatment period as described above will be listed but not summarized.

Modified Treatment Period

For patients whose treatment is suspended due to undetectable PSA at week 36 the modified period is defined as the period of time of study drug exposure starting from the date of the first dose of study drug through 30 days after last dose prior to the treatment suspension PLUS the time period starting from date of first dose at study drug reinitiation through a minimum of 30 days after last dose of study treatment, or the start day of new antineoplastic drug therapy -1 day. If date of first dose at study drug reinitiation is earlier than 30 days after last dose prior to the treatment suspension, then the modified treatment period is the same as that on-treatment period.

For all other patients the modified treatment period is the same as the on-treatment period.

Reinitiation Treatment Period

The reinitiation treatment period is defined only for patients who suspend treatment due to undetectable PSA at week 36 and subsequently reinitiate treatment and is defined as the time

period starting from date of first dose at study drug reinitiation through minimum 30 days after last dose of study treatment, or start day of new antineoplastic drug therapy -1 day.

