Treatment-Emergent Adverse Events

Treatment-emergent adverse events (TEAEs) are those events with onset dates occurring during the on-treatment period for the first time

Modified Treatment-Emergent Adverse Events

Modified treatment-emergent adverse events (mTEAEs) are adverse events occurred during the modified treatment period (ie, events occurring or worsening during the treatment suspension period after 30 days of last dose prior to treatment suspension (and prior to treatment suspension if applicable) are excluded).

Reinitiation Treatment-Emergent Adverse Events

Reinitiation treatment-emergent adverse events (rTEAEs) are adverse events occurred for the first time during the dosing period after suspension and reinitiation of study treatment as defined by the reinitiation treatment period.

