4.2. Safety Analysis Set

The safety analysis set will include all randomized patients who receive at least 1 dose of any study drug. Unless otherwise specified, all safety analyses will use the safety population according to the actual treatment received (not the treatment assigned).

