6.8. Safety Summaries and Analyses

All patients in the safety population will be used in the safety analyses. Safety analyses will be summarized by treatment group.

The on-treatment period will be defined as in Section 5.2.5. For incomplete date of last dose of study drug and incomplete start date of the first new antineoplastic treatment that are missing the day of the month, please refer to the missing data Section 5.3.1.

At the time of analyses after protocol amendment #5, safety data for the patients treated in protocol defined open-label (OL) stage will be summarized by double blinded stage and OL stage separately.

At the time of analyses after protocol amendment #5, based on the protocol defined data collection, safety will be evaluated by the frequency of serious adverse events, frequency and severity of adverse events, frequency of study drug discontinuation due to adverse events, and frequency of new clinically significant changes in clinical laboratory values and vital signs.

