6.8.1. Adverse Events

The severity of all adverse events is to be evaluated by the investigator based on the NCI CTCAE version 4.03. All adverse events will be coded to preferred term (PT) and system organ class (SOC) using MedDRA version in use at the time of database release.

TEAEs will be summarized by PT and/or SOC, toxicity grade, and relationship to study treatment. An event will be considered treatment related if the investigator considered the event related to one or both of study drugs given in combination. The treatment related summaries will be separated for one or both study drugs when given in combination.

Separate summaries will be provided for serious TEAEs regardless of causality and serious TEAE related to study treatment.

Separate summaries will be provided for TEAEs (regardless of relationship to study treatment):

- Leading to permanent discontinuation from enzalutamide,
- Leading to permanent discontinuation form leuprolide,
- Leading to enzalutamide dose interruptions,
- Leading to leuprolide dose interruptions,
- Leading to enzalutamide dose reductions, and
- Leading to leuprolide dose reductions.

mTEAEs and rTEAEs defined as in Section 3.5 will be summarized by toxicity grade and relationship to study treatment. Separate summaries will also be provided for:

- Serious mTEAE regardless of causality,
- Serious mTEAE related to study treatment,
- Serious rTEAE regardless of causality, and
- Serious rTEAE related to study treatment.

Patients with multiple occurrences of events for a given PT, SOC will only be counted once.

Adverse event time-adjusted rates will be calculated as the number of occurrences of event divided by the number of patient-years of treatment-emergent (for the corresponding treatment emergent period)surveillance for each treatment group. Patients can have more than 1 occurrence of each event.

Additionally, Kaplan-Meier methods will be used to display the time to the first Grade 3 or higher TEAE by treatment group. Patients who are not known to have had Grade 3 or higher TEAE by the analysis cutoff date are censored at the date last known to be Grade 3 or higher TEAE-free. Kaplan-Meier methods will also be used to display the time to the first SAE by treatment group. Patients who are not known to have had SAE by the analysis cutoff date are censored at the date last known to be SAE-free.

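### By default, percentages for adverse events on re-treatment (rTEAEs) would be divided by all safety patients, although only men who restarted drug can have one, so the re-treatment risk is understated

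*SAP*

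**What the plan says.** SAP 5.2.6 opens its list of conventions with "Unless otherwise specified, the following conventions will be applied to all analyses". One of them fixes the denominator for safety tables: "For safety analyses, percentages will be calculated based on the number of patients in the analysis population in each treatment group". Another asks for counts and percentages for categorical endpoints.

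The analysis population is set in two places. SAP 4.2 says "The safety analysis set will include all randomized patients who receive at least 1 dose of any study drug", and SAP 6.8 adds "All patients in the safety population will be used in the safety analyses". SAP Section 4 defines the ITT, safety and evaluable ITT sets and no set of re-treated patients.

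SAP 3.5 defines three safety periods. The third is restricted: "The reinitiation treatment period is defined only for patients who suspend treatment due to undetectable PSA at week 36 and subsequently reinitiate treatment". An rTEAE is an event that first occurs in that period.

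For reporting, SAP 6.8.1 says "mTEAEs and rTEAEs defined as in Section 3.5 will be summarized by toxicity grade and relationship to study treatment", and lists separate summaries of serious rTEAEs, overall and treatment-related. It gives no denominator for them.

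**The concern.** Two kinds of men cannot have an rTEAE: those who never suspended, and those who suspended and have not restarted. Under the default rule both stay in the denominator and count as event-free, so the percentage mixes how often re-treated men have events with how often men are re-treated at all.

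A single suspension followed by possible reinitiation is a central feature of the design. A clinician reading an rTEAE table wants to know how often a man who restarts his assigned treatment has an event, and a figure diluted by men who never restarted answers a different question. The dilution also depends on PSA response after randomization. Undetectable PSA at week 36, which determines suspension, is itself an endpoint compared between arms (SAP 6.3.4), so equal restart shares cannot be taken for granted.

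**Working it through.** **Which denominator applies.** The default in SAP 5.2.6 holds unless another rule is given. SAP 6.8.1 gives none for rTEAEs. The SAP does restrict denominators elsewhere:

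- Table 10 divides TEAEs in each study-day category by the men still on treatment when that category begins.
- SAP 3.2.2.2 and 3.2.2.3 divide the 2-year proportions by suspended patients only.
- The time-adjusted rates in SAP 6.8.1 use patient-years from the matching treatment-emergent period.

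None of these rules reaches the rTEAE percentages, so the default stands.

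**The identity.** For one arm, let N be the safety patients, R those who restarted, and x the restarters with at least one rTEAE. Then

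x/N = (x/R) × (R/N)

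The left side is the percentage under the default, and x/R is the risk among re-treated men. The understatement factor is (x/R) ÷ (x/N) = N/R. It does not depend on the risk and exceeds 1 whenever R < N.

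**Size.** The plan states no rTEAE rate, number suspended or number restarted, so there is no figure of its own to reproduce. The table assumes N = 350 (the protocol's planned number per group; the size of the safety set is not given), a re-treatment risk of 20%, and a range of restart shares.

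| Restart share R/N | R | x = 0.20 × R | Default x/N | Among restarters x/R | Factor N/R |
|---|---|---|---|---|---|
| 30% | 105 | 21 | 6.0% | 20.0% | 3.33 |
| 50% | 175 | 35 | 10.0% | 20.0% | 2.00 |
| 70% | 245 | 49 | 14.0% | 20.0% | 1.43 |
| 90% | 315 | 63 | 18.0% | 20.0% | 1.11 |

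**Between arms.** Suppose both arms have a re-treatment risk of 20%.

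- Restart shares of 50% and 70%: 0.20 × 0.50 = 10.0% and 0.20 × 0.70 = 14.0%, a ratio of 1.40 with no difference in risk per re-treated man.
- Restart shares of 80% in both: 16.0% in each arm, understated but with no distortion between arms.

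**Direction.** R/N is the share who suspend multiplied by the share of those who restart. A more effective arm may suspend more men, which raises R/N, and restart fewer of them, which lowers it. The sign of the net effect cannot be settled from the documents.

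**The case against.** The case on the other side has five parts.

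*The denominator is inferred.* No sentence says that rTEAE percentages use the whole safety population. SAP 6.8.1 points back to SAP 3.5, where the period is confined to restarters, and Table 10 shows that the safety section is not rigid about denominators. A programmer might build the table on restarters. This stands as a limit on the wording: the default leads to N, but the plan does not say so for rTEAEs by name. It does not remove the point, because the written rule gives N and nothing displaces it.

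*Re-treatment safety is described elsewhere.* A reader might infer that the rTEAE percentages are the only account of safety on a second course. They are not: the time-adjusted rates use re-treatment time and avoid the dilution. But they count occurrences per patient-year, and one man can contribute several, so they do not say how many men were affected.

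*R can be recovered.* SAP 6.7.4 summarizes duration of treatment after reinitiation, SAP 5.2.5 sets it to missing for men who did not restart, and SAP 5.2.2 asks for the number of nonmissing values. A careful reader could therefore work out x/R. That is true, and it makes this a matter of presentation rather than lost information, but the table should not need that repair.

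*x/N is a legitimate quantity.* It is the share of all treated men who have a new event on re-treatment under the suspend-and-restart strategy, and it keeps essentially the randomized groups, whereas x/R conditions on a subset formed after randomization. This is correct. x/N is simply not the risk of re-treatment, and the table gives no warning of the difference.

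*Open-label tables.* A reader might extend the point to the open-label stage. The documents do not support that: protocol 18.9 and SAP 6.8 already confine those summaries to patients treated in that stage.

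**Conclusion.** The point holds as a specification problem in descriptive safety tables. Following the SAP as written, rTEAE and serious rTEAE percentages understate the risk among re-treated men by the factor N/R in each arm. That rests on the default denominator being applied and on at least some safety patients not restarting. The size is unknown; the factors of 3.33 to 1.11 come from assumed restart shares of 30% to 90%.

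A reader might also infer that the factor differs between arms, or that the more effective arm would look safer on re-treatment. The documents support neither as fact. Distortion between arms follows only if restart shares differ, its direction is unknown, and it vanishes if they are equal.

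Overall TEAE and modified TEAE percentages are not affected by this mechanism, since every treated man has those periods. No hypothesis test depends on rTEAEs. The change is still worth making, because the present rule gives a figure that is easily misread in the favourable direction.

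**What to change.** In SAP 6.8.1, state that percentages of rTEAEs and serious rTEAEs use as denominator the safety patients in each arm who received at least one dose at reinitiation. Show that number in the column header. Label between-arm rTEAE differences as descriptive, because the re-treated group is defined after randomization.

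The cost is a short addition to the SAP and a changed denominator in the rTEAE tables. No new data are needed, since SAP 5.2.5 already separates men who restarted from those who did not. The percentages become larger and so less favourable, and any comparison between arms then rests on a subset that randomization does not protect. Tables already produced on the whole safety population can be restated by dividing the same patient counts by R.
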